## SECTION V: RESEARCH PLAN

1. **Statement of Purpose:** State the scientific aim(s) of the study, or the hypotheses to be tested. Alcoholism is a disorder that is mediated by multiple genes and environmental factors. Existing medications like naltrexone and acamprosate are not efficacious in all drinkers. Therefore, we need to develop new and effective strategies to treat alcoholism. Development of medications for this disorder should be based on our understanding of the behavioral and neurochemical mechanisms mediating alcohol reward and drinking. There is extensive preclinical evidence suggesting that glutamatergic circuits are involved in the acute behavioral effects of alcohol as well as in alcohol tolerance and withdrawal. This project will evaluate the effect of an agent that indirectly modulates NMDA-R signaling without directly antagonizing NMDA-Rs on alcohol drinking. Specifically, we will test the influence of Saracatinib, a Src/Fyn protein tyrosine kinase inhibitor that modulates NMDA-R signaling via Fyn inhibition.

**Primary Aim 1:** To evaluate the effects of Saracatinib (125 mg/day) versus placebo on alcohol craving.

*Primary hypothesis 1a:* Saracatinib (125 mg/day) will reduce craving for alcohol after exposure to the priming drink of alcohol, and during the free-choice drinking period, when compared with placebo.

**Primary Aim 2:** To evaluate the effects Saracatinib (125 mg/day) versus placebo on alcohol drinking

*Primary hypothesis 1b:* Saracatinib (125 mg/day) will reduce number of drinks consumed during the free-choice drinking period, when compared with placebo.

**Secondary Aim 1:** To evaluate the effects of Saracatinib (125 mg/day), versus placebo, on alcohol-induced stimulation and sedation during the ADP.

**Secondary Aim 2:** To examine the tolerability of Saracatinib (125 mg/day) in heavy drinkers.

**Exploratory Aims:** To explore predictors of Saracatinib response. The predictors have been selected based on findings from our earlier work and include behavioral outcomes like impulsivity, habit and deficiency in loss-avoidance learning, genetic markers related to alcohol drinking or glutamate and Src/Fyn systems, and neural networks/markers identified using multimodal neuroimaging.

2. **Background:** Describe the background information that led to the plan for this project. Provide references to support the expectation of obtaining useful scientific data.

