### **Alcohol Drinking Paradigm (ADP)**

The procedures for both ADP's will be similar and will follow the NIAAA guidelines for administering alcohol to humans (<http://www.niaaa.nih.gov/research/guidelines-andresources/administering-alcohol-human-studies>). Participants will arrive at the HRU of YNHH at 10 am for ADP1 and 10:30am for ADP2. They will be told not to consume any alcohol after 10 pm on the earlier evening. We will assess breath alcohol levels and urine drug tests. If the breath alcohol levels are positive but below 0.05 and decreasing, the participant will be allowed to continue. If the urine drug tests are positive and/or breath alcohol levels are 0.05 or greater, the session will be rescheduled. The drinking sessions will be conducted in a private room in the HRU. Because caffeine is a weak phosphodiesterase inhibitor (Nehlig et al., 1992), caffeine users will be limited to one serving of their usual caffeinated beverage with lunch at 12 pm. This will also help to avoid caffeine withdrawal.

The ADP will start at 3 pm with the priming dose period, which will be followed by 3, 1 hour drinking periods (4-5 pm, 5-6 pm and 6-7pm) and will conclude at 7 pm (see Table 1 for detailed list of procedures).

- a. ***Exposure to Alcohol Cue:*** Ten minutes prior to the start of the priming dose period (i.e. 2:50 pm), the RA will enter the participant's room with the alcohol dose and the preferred

mixer. The RA will then proceed to mix the priming drink in front of the participant. When done, he/she will leave the drink on the table, instruct the participant not to drink the priming drink yet, and leave the room. At 2:59 pm the RA will reenter the room, ask the subject to report on how much they are craving alcohol, and then tell the participant that they have five minutes to consume the priming drink and will then again leave the room.

- b. *Priming Dose (PD) Period:* This dose provided at 3 pm will raise blood alcohol levels to 0.03mg% and subjects will have 5 minutes to drink it. The purpose of the PD is to provide a standard dose for evaluating the effects of medications and to model a "lapse" situation. A 40-minute absorption period will follow during which the subjective and physiological effects of this priming dose of alcohol in combination with Saracatinib will be monitored. Using this procedure, we will be able to closely monitor changes in subjective effects of alcohol during the rising and falling limbs of the blood alcohol curve.

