- c. *Alcohol Self-Administration (SA) Periods:* Following the PD, there will be 3, 1-hour SA periods. During each SA period, participants will be offered a choice between 4 alcoholic drinks designed to raise BALS by 0.015 mg% of alcohol, or cash (equivalent to the price of each drink that is not consumed). The first SA period will begin at 4:00 pm when the RA will take 4 prepared drinks into the room along with a "tab" sheet worth \$12. The participant will be informed that these 4 drinks will be available to him/her for the next 60 minutes (i.e. until 5 p.m.). S/he can either choose to drink or keep the money; each drink will cost \$3. The money will be given to them the next morning before they leave the hospital. The second and third SA period will begin at 5 p.m. and 6 p.m. respectively will be similar to the SA period. Thus, participants can choose to consume up to 12 additional drinks over these 3 SA periods or receive up to \$36. *Given the possibility that a participant could consume more alcohol during the ADP than what they might normally consume, all subjects will be closely monitored and the ADP will be stopped if 1) The subjects requests to stop, 2) In the judgment of trained research personnel conducting the study and monitoring subject behavior the study needs to be stopped, or 3) If the subject's heart rate exceeds their maximum heart rate (220 minus age).*
- d. *Beverage Content and Mixers:* The YNHH Investigational Pharmacy will calculate the alcohol dose based on the age, weight and gender of the participant (Watson, 1989) and deliver the doses to the HRU. The PD will raise blood alcohol levels to 0.03 mg% and each drink in the SA periods will raise BAL by 0.015 mg%. Alcoholic beverages administered during this study will consist of 1 part 80 proof liquor of the subject's choosing to 3 parts mixer chosen from a selection of equicaloric noncaffeinated noncarbonated beverages. The RA will prepare the drinks using the alcohol doses prepared by the YNHH pharmacy. Participants would have already chosen their mixers on an earlier day, thereby providing a closer approximation to their own drinking experiences. Frozen plastic cubes will be used to chill each drink without diluting them and the prepared drinks will be covered with saran wrap to avoid any evaporation of alcohol.

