**Statistical analyses:** All data will be transcribed onto teleforms, checked for completeness and clarity, and sent to the data manager, [name]. All outcomes will be summarized descriptively and assessed for normality prior to analysis using normal probability plots and Kolmogorov test statistics. Transformations or nonparametric analyses will be performed as necessary. In the mixed models described below, the correlation between repeated measures on an individual will be modeled using random effects and/or structured variance-covariance matrices. The best fitting variance-covariance structure will be determined by information criterion. The mixed effects approach is advantageous in that it is unaffected by randomly missing data and allows greater flexibility in modeling the correlation structure of repeated measures data (Gueorguieva & Krystal 2004). All tests will be two-sided and considered statistically significant at  $\alpha=0.05$ . Significance levels for secondary comparisons will be adjusted for multiple tests using the Bonferroni correction, basing the adjustment on the number of conceptually related statistical tests within each hypothesis.

**Aim 1:** Scores on the Yale Craving Scale will represent the dependent variable in a linear mixed model with treatment (0 or 125 mg Saracatinib) as a between-subjects factor and time (see time points, Table 1) and session (baseline, post-treatment) as within-subject factors. All multilevel interactions will be modeled and interpreted by plotting and comparing least squares means. We anticipate a significant treatment by time by session interaction explained by greater posttreatment reductions in craving with Saracatinib compared to placebo. We will also explore the influence of

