treatment on alcohol craving in response to the alcohol cue exposure just prior to the start of the drinking session using a similar model. In the above models, treatment will be considered as a categorical predictor but linear and quadratic effects of dose will also be tested. **Aim 2:** Total number of drinks consumed during the ADP will be compared among treatment conditions using linear mixed models as above with treatment (0 mg or 125 mg Saracatinib) as a between-subjects factor and session (baseline, post-treatment) as a within-subject explanatory factor. We anticipate a significant treatment by session interaction owing to reduced drinking following Saracatinib treatment, but not placebo. We will also consider change from baseline as the outcome measure and compare the treatment groups using ANOVA.

**Secondary Aim 1:** Alcohol-induced stimulation and sedation during ADP will be evaluated using the same linear mixed models outlined in Specific Aim 1, with BAES subscale scores as the dependent variables.

**Secondary Aim 2:** Adverse events will be recorded and summarized qualitatively by treatment group. Total and severe adverse event frequencies will be compared between groups using chisquare or Fisher's exact test. Similar to what our collaborators, Drs. [name] and [name] observed among AD subjects (see preliminary data), we anticipate AE profiles of the two active Saracatinib groups will be similar to placebo. Vital signs and blood alcohol levels and plasma Saracatinib levels assessed during the ADP will also be evaluated using linear models to examine alcohol-Saracatinib interactions.

**Exploratory Aims:** All measures (e.g., PST, Habit, genetic markers, neural markers) will be evaluated using the same models outlined in Specific Aim 2.

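### Hypothesis 1a predicts lower craving, but the only supporting result named for Aim 1 is a three-way interaction that tests the time course, and the plan does not say which term decides 1a

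*Combined protocol and SAP*

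**What the plan says.** Section V, item 1 (Statement of Purpose) gives primary hypothesis 1a: compared with placebo, saracatinib "will reduce craving for alcohol after exposure to the priming drink of alcohol, and during the free-choice drinking period". This is a statement about the level of craving in two windows. It says nothing about the shape of the curve within a session.

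Section V, item 11 (Statistical analyses, Aim 1) fits a linear mixed model to the Yale Craving Scale, with treatment between subjects and time and session within subjects. On interpretation it says "All multilevel interactions will be modeled and interpreted by plotting and comparing least squares means", and then "We anticipate a significant treatment by time by session interaction explained by greater posttreatment reductions in craving with Saracatinib compared to placebo". For drinking, Aim 2 says "We anticipate a significant treatment by session interaction owing to reduced drinking following Saracatinib treatment, but not placebo". Secondary Aim 1 applies the Aim 1 models to alcohol-induced stimulation and sedation.

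The rating times are in Table 1, which is not in the available text. The Alcohol Drinking Paradigm section describes a rating at 2:59 pm, before the priming drink, when staff "ask the subject to report on how much they are craving alcohol". Item 11 explores craving in response to the "alcohol cue exposure just prior to the start of the drinking session using a similar model". The Assessments section has craving rated every thirty minutes over the three choice hours.

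**The concern.** In this model the treatment-by-session term compares the arms on the baseline-to-post-treatment change in craving, averaged over ratings. That is what 1a predicts. The three-way term compares the arms on how that change varies from one rating to the next. The two can disagree in both directions: a steady reduction leaves the three-way term at zero, and an effect that changes sign over the session can make it significant with no average benefit.

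The plan names only the three-way result, explains it in words that describe treatment-by-session (a larger reduction on drug), and gives no rule for a disagreement. The test of a primary hypothesis could then be chosen after the data are seen. The same ambiguity carries over to the stimulation and sedation scores.

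**Working it through.** **Inputs from the documents (Section V, item 11).** 52 completers at about 2:1, taken as 35 active and 17 placebo; two-sided alpha 0.05; d=0.8; stated power 80%.

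**Assumed.** The documents give no craving effect size and no correlation between craving changes, so d=0.8 is placed on the mean change over ratings. Number of ratings T = 7 to 12: six from half-hourly ratings over three hours, plus one to six others. Changes (post-treatment minus baseline) have equal correlation ρ (compound symmetry).

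**1. The plan's own power figure.** With m = 35×17/52 = 11.44, the noncentrality is 0.8×√11.44 = 2.706 on 50 df, critical t 2.009. Power is 75.6% by noncentral t and 77.2% by normal approximation. A 34:18 split gives 76.8% and 78.4%. The stated 80% is not quite reached at 2:1 (26:26 gives 80.7%, 40:20 gives 81.9%). That is a separate matter. What counts here is that the figure is for a two-group difference, which corresponds to treatment-by-session and not to the three-way term.

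**2. Equal reduction at every rating.** Treatment-by-session is a two-sample t test on the mean change: 75.6%. For the three-way term, with δ_t the drug effect at rating t,

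λ = m × Σ(δ_t − mean δ)² / [σ²(1 − ρ)].

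If all δ_t are equal, λ = 0 and the rejection rate is alpha, 5%, whatever T or ρ. Simulation (20,000 runs; T = 4, 7, 10; ρ = 0.3, 0.5, 0.7) gave 75-76% and 4-5%.

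**3. No net reduction, effect crossing from harm to benefit.** With amplitude 0.6 SD and ρ = 0.5, simulation gave about 5% for treatment-by-session and 96-99% for the three-way term.

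**4. Linear rise from (1−s)d to (1+s)d.** Treatment-by-session stays at 76%, because the mean is unchanged. Example for the three-way term with T = 9, ρ = 0.5, s = 0.5, σ = 1:
- SD of the mean change = √[(1 + 8×0.5)/9] = 0.745, so the mean effect is 0.8×0.745 = 0.596.
- Squared deviations sum to 0.9375×0.596² = 0.333.
- λ = 11.44×0.333/0.5 = 7.63; F on 8 and 400 df; power 45%.

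Repeating this over T = 7 to 12, with both the repeated-measures F and Hotelling's T², and solving for the growth (1+s)/(1−s) at which the three-way term also has 75.6%:

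| ρ | Three-way power, rise from 50% to 150% of d | Break-even growth, first to last rating |
|---|---|---|
| 0.3 | 18-22% | 33-fold or more |
| 0.4 | 27-33% | 8- to 16-fold |
| 0.5 | 38-48% | 4.7- to 6.7-fold |
| 0.6 | 54-68% | 3.3- to 4.2-fold |
| 0.7 | 75-89% | 2.5- to 3.0-fold |
| 0.8 | 95-99% | 2.0- to 2.3-fold |

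Below break-even, treatment-by-session is the stronger test of the two; above it, the three-way term is.

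**The case against.** The strongest reply is that the plan already covers this. All interactions are modelled, least squares means are compared, and the expected result is tied to larger reductions on drug. The sentence in question is a forecast; it does not make the three-way term a gate. All of that stands. A reader might infer that the analysis would miss a steady reduction, or that 1a is to be judged at 5% power. The documents do not support either: treatment-by-session would be estimated, and nothing says 1a fails without the three-way term. What remains is that no term is designated.

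Second, a constant effect is the case least favourable to the three-way term, and a varying effect is plausible because "participants can choose to consume up to 12 additional drinks over these 3 SA periods", so alcohol exposure may diverge between arms. This stands too. A reader might infer that treatment-by-session is always the more powerful choice; the table shows that it is not.

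Third, Table 1 is unseen. If it includes a rating before any alcohol, a drug effect on the response to priming would show up partly as a three-way interaction. The separate cue-craving model suggests that the 2:59 pm rating lies outside the Aim 1 model but does not establish it.

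Fourth, the contrast with Aim 2 is weak evidence that the wrong term was picked. Total drinks is one value per session, so treatment-by-session is the only interaction available there.

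**Conclusion.** The point holds as a gap in pre-specification. The mismatch is clear from the text: 1a concerns the level of craving, the one named result concerns its time course, and no rule says which term answers 1a.

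The size depends on an unknown time course. Under a constant reduction, the named term rejects in 5% of trials against about 76% for treatment-by-session. Under a linear rise, the three-way term overtakes somewhere between about 2-fold growth (correlation 0.8) and 8-fold or more (0.4 or below). These figures rest on 35 versus 17 completers, d=0.8 on the mean change, 7 to 12 ratings and compound symmetry, of which only the sample size, the approximate ratio and d itself come from the documents, and d is not tied there to craving. Confidence is high for the mismatch and lower for the power consequences. It should be fixed because it concerns the test of a primary hypothesis.

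**What to change.** In Section V, item 11, Aim 1, name as the primary test of 1a the 1-df treatment-by-session contrast (post-treatment minus baseline, active minus placebo), averaged with equal weight over the post-priming and free-choice ratings and excluding any pre-drink rating. Report the same contrast for each of the two windows as secondary, under the rule the plan already has: "Significance levels for secondary comparisons will be adjusted for multiple tests using the Bonferroni correction". With two tests that is 0.025 each. Keep the three-way interaction as a description of the time course. State whether Secondary Aim 1 follows the same rule.

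The cost is one or two sentences and one contrast on a model already planned, with no new data. The downside is less power than the three-way test if the effect varies strongly over the session, from about 2-fold growth upward depending on the within-subject correlation.

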The current proof-of-concept trial will test the effects of 125 mg dose of Saracatinib versus placebo on alcohol drinking behaviors using the ADP. We have determined that there is a need to focus on the 125 mg dose and that there is no advantage to testing a lower dose (50 mg) of the drug as proposed in the grant. The 50 mg dose is known to be inferior to the 125 mg in terms of Src family target coverage both peripherally and centrally and therefore the pharmacologic effect of the 50 mg dose should not be superior to the 125 mg dose. In addition, this will also allow Astra Zeneca to provide us with the 125 mg and matching placebo over a 3-year period without having to conduct additional stability testing over an extended period of time. Therefore, with the goal of getting this proof of principle trial done in an efficient manner, we will now focus on an adequately powered examination of the 125 mg dose, the dose we believe will be effective based on our preliminary data and knowledge of target engagement. Specifically, in the first three years of the grant, we will recruit 60 subjects and randomize 40 subjects to the 125 mg Saracatinib dose and 20 subjects to placebo. We anticipate a 10% drop out, leaving a final sample of 50 completers.

Thus, 60 non-treatment seeking, heavy drinkers will receive Saracatinib (0 or 125 mg/day), stratified by gender(to achieve 50 completers). Subjects will participate in a baseline ADP, followed by seven days of treatment with the study medication, and then a second ADP when they will take their last dose of study medication. Drinking behavior, alcohol craving and alcohol-induced stimulation/sedation will be measured in each ADP. Adverse events and drinking will be monitored during the treatment period, and at follow up. Potential behavioral predictors of Saracatinib response will be obtained at baseline and post-treatment ADP, and the CTNA core assessment battery will be obtained at baseline.

2. **Research Plan:** Summarize the study design and research procedures using non-technical language that can be readily understood by someone outside the discipline. **Be sure to distinguish between standard of care vs. research procedures when applicable, and include any flowcharts of visits specifying their individual times and lengths.** Describe the setting in which the research will take place.

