**B.** What are the conditions or procedures for sharing of materials and/or distributing for future research projects? Genetic testing will only be conducted for research purposes and the results will be available to investigators on this study. Eventually, DNA extracted may be available to any qualified researcher; so will some of the genetic information from the DNA.

**C.** Is widespread sharing of materials planned? Yes

**D.** When and under what conditions will materials be stripped of all identifiers? The PI will retain identifiable information about each sample that is collected. The samples identified by code and stripped of any identifiers prior to being transported to [name] lab. All samples are made anonymous prior to distribution. Some of the investigators may have commercial interests.

- E. Can donor-subjects withdraw their materials at any time, and/or withdraw the identifiers that connect them to their materials? Donors will be told during the consenting process that they can choose to withdraw their materials at any time.
  - i. How will requests to withdraw materials be handled (e.g., material no longer identified: that is, anonymized) or material destroyed)? Donors will be told to contact the PI directly to request withdrawal of participation
- F. Describe the provisions for protection of participant privacy. The PI will retain identifiable information about each sample that is collected. The samples identified by code and stripped of any identifiers prior to being transported to [name] lab.
- G. Describe the methods for the security of storage and sharing of materials. The identifiers will be stored in a locked file cabinet at the PI's office.

**4. Subject Population:** Provide a detailed description of the types of human subjects who will be recruited into this study.

Approximately 90 male and female non-treatment seeking alcohol dependent volunteers will be recruited and evaluated for eligibility. We anticipate that 60 will complete the baseline ADP and be randomized to one of two medication groups. Based on our current experience, we anticipate a final completer sample of 50 heavy drinkers will complete the baseline ADP, the drug administration period and the second ADP.

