**4.b. Frequency of Review of Safety Reports**

Subjects are recruited at a maximum rate of 2 per month; thus, the DSMB will review safety reports two times a year. More frequent meetings will be scheduled if indicated by interim findings.

- d. For multi-site studies for which the Yale PI serves as the lead investigator: N/A
  - i. How will adverse events and unanticipated problems involving risks to subjects or others be reported, reviewed and managed?
  - ii. What provisions are in place for management of interim results? iii. What will the multi-site process be for protocol modifications?

**11. Statistical Considerations:** Describe the statistical analyses that support the study design.

**Power Calculations:** We will recruit up to 90 subjects and randomize 40 subjects to the 125 mg Saracatinib dose and 20 subjects to placebo. We will use the number of drinks consumed at the baseline session (5 or less, 6 or more) and gender as stratification variables in the randomization. 6 drinks is half the total number of drinks they are allowed to drink in the self-administration period and will allow the participant to reach a BAC of 0.07 or higher which is the threshold for heavy drinking. We anticipate that we will obtain complete data on 52 subjects in approximately 2:1 ratio on active vs. placebo. This would give us 80% power to detect large effects of drug ( $d=0.8$  or greater) at two-sided alpha level of 0.05. Such an effect size is considered clinically meaningful and is consistent with our pilot data where we observed large effects of the 125 mg dose (administered over eight days) on alcohol-induced stimulation and feeling intoxicated and feeling good (all  $>0.8$ ) following exposure to a fixed dose of alcohol (0.8 mg/kg) in heavy social drinkers. Randomizing more subjects on active drug will allow us to explore relationships between potential predictors (e.g. gender, smoking status) and outcome in the treatment group. Thus, we will be well powered with our proposed sample to detect clinically relevant effects of Saracatinib.

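### Aim 2 drinks: the planned tests are valid, but adjusting for baseline-session drinks would add power at almost no cost when the two sessions are weakly to moderately correlated

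*Combined protocol and SAP*

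**What the plan says.** Drinks during the free-choice period are one of two primary outcomes (Section V.1). Under Statistical analyses in Section V.11, Aim 2 fits a linear mixed model to total drinks "with treatment (0 mg or 125 mg Saracatinib) as a between-subjects factor and session (baseline, post-treatment) as a within-subject explanatory factor". The test of interest is stated directly: "We anticipate a significant treatment by session interaction owing to reduced drinking following Saracatinib treatment, but not placebo". A second analysis follows: "We will also consider change from baseline as the outcome measure and compare the treatment groups using ANOVA". The text does not say which of the two decides the aim. For mixed models generally, "The best fitting variance-covariance structure will be determined by information criterion".

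Baseline-session drinks therefore enter as one of two outcome values, never as a covariate. Yet Power Calculations in the same section uses the "number of drinks consumed at the baseline session (5 or less, 6 or more) and gender as stratification variables in the randomization". Section V.2 (Background) names gender only: "stratified by gender(to achieve 50 completers". Neither factor appears in the Aim 2 model.

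**The concern.** With two sessions and complete data, the interaction test and the change-score ANOVA are the same test, so the second analysis adds no protection. Both subtract the whole baseline value. That is efficient only when the sessions are highly correlated. At lower correlation the subtraction adds noise, and below 0.5 (equal SDs) it is worse than ignoring baseline altogether.

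Stratifying on baseline drinks does not recover the loss. It balances the arms, but a model without baseline as a covariate does not credit that balance in its standard error.

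At stake is power for a primary outcome with about 17 placebo completers, when the missing covariate is already recorded before randomisation.

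**Working it through.** **Inputs from Section V.11.** 40 active and 20 placebo randomised; two-sided alpha 0.05; d = 0.8; stated power 80%; and "We anticipate that we will obtain complete data on 52 subjects in approximately 2:1 ratio on active vs. placebo", for which the nearest whole split is 35:17. Drinks range from 0 to 12 (Section V, Alcohol Self-Administration Periods).

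**Assumed, because the documents do not give them.** The between-session correlation (rho); the SDs; and the scale of d, taken first as SDs of a single session.

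**1. The plan's own figure.** A two-sample comparison at 35:17 with d = 0.8 gives 77.2% (normal) or 75.6% (t, 50 df), a little under the stated 80%. What follows does not depend on this gap.

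**2. Closed form (equal session SDs, no stratification on baseline).**
- Change score: variance factor 2(1 − rho), so effective d = 0.8/√(2(1 − rho)).
- Adjusted for baseline: variance factor 1 − rho², so effective d = 0.8/√(1 − rho²).
- Variance ratio, adjusted to change: (1 + rho)/2.

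| rho | variance ratio | effective d, change | effective d, adjusted | power, change | power, adjusted |
|---|---|---|---|---|---|
| 0.3 | 0.65 | 0.676 | 0.839 | 61.1% | 79.4% |
| 0.5 | 0.75 | 0.800 | 0.924 | 75.6% | 86.5% |
| 0.7 | 0.85 | 1.033 | 1.120 | 92.9% | 96.0% |
| 0.8 | 0.90 | 1.265 | 1.333 | 98.7% | 99.3% |

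To match the adjusted analysis by recruitment, the change score would need about 52/0.65 = 80 completers at rho 0.3, 52/0.75 = 69 at 0.5 and 52/0.85 = 61 at 0.7.

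**3. Simulation of the planned procedure.** 60 subjects were randomised 2:1 in blocks of 6 (assumed). Drinks were bivariate normal, rounded and clipped to 0–12, with mean 6, baseline SD 3, 50% women and an effect of 0.8 × 3 = 2.4 drinks. Second sessions were missing at random. The mixed model was fitted by REML with all 60 baselines, and AIC chose between compound symmetry and unstructured covariance. Each cell had 10,000 trials (5,000 in E). Monte Carlo SE is about 0.5 points for power and 0.2 for type I error.

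Power (%), planned mixed model / regression on baseline drinks and gender:

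| Scenario | rho 0.3 | 0.4 | 0.5 | 0.6 | 0.7 | 0.8 |
|---|---|---|---|---|---|---|
| A: drinks and gender strata, 52 completers, equal SDs | 63/79 | 69/81 | 76/86 | 84/90 | 92/95 | 98/99 |
| B: as A, gender strata only | 62/78 | 68/81 | 75/85 | 83/89 | 92/95 | 98/99 |
| C: as A, 50 completers | 62/77 | 68/80 | 75/84 | 83/88 | 91/94 | 98/99 |
| D: as A, post-treatment SD 3.9 | 46/56 | 51/59 | 58/63 | 67/69 | 76/77 | 89/89 |
| E: as A, post-treatment SD 2.4 | 76/93 | – | 87/96 | – | 97/99 | 99.5/100 |

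Before rounding, the gain in A is 16, 12, 9, 5, 3 and 1 points. The change-score ANOVA in A has 61, 68, 75, 83, 91 and 98%.

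**4. Where the loss appears.**
- With baseline drinks as a stratum (A), the planned standard error is too large: its ratio to the true SD under the null runs from 1.108 at rho 0.3 to 1.033 at 0.8. Type I error is 3.1–4.5%, so the test is conservative.
- With gender strata only (B), that ratio is 0.987–1.005 and type I error is 4.7–5.5%. Here the estimate itself is noisier: the adjusted estimator has 0.70 of the variance of the compound-symmetry mixed-model estimator at rho 0.3 and 0.91 at 0.8.
- The adjusted analysis has type I error of 5.0–5.5% in A.

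**5. Which covariate matters.** Adding gender as a main effect to the planned model leaves the mean standard error at 0.975 (rho 0.3). Dropping gender from the regression changes power by at most 0.4 points, or 0.9 with a 1.5-drink gender difference. The gain comes from baseline drinks.

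**The case against.** The strongest reply is that nothing here is wrong. The planned test is valid, targets the same treatment effect and matches the stated hypothesis. The size of the benefit depends on quantities the documents do not give. The same people repeat a similar session after 7–10 days of treatment, so a high correlation is at least as plausible as 0.3. In scenario A the plan already exceeds its 80% target from rho 0.6 upward. All of that stands, and it is why this is an improvement and not a correction.

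The scale of d is also open. If d = 0.8 is in change-score SDs, the planned analysis has 75.6% power at every rho, while the adjusted analysis has 90.8% at rho 0.3, 86.5% at 0.5, 82.0% at 0.7 and 79.8% at 0.8. The pattern across rho changes, but adjustment is ahead on both readings.

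The point at which the gain becomes negligible depends on the shape of the data. With an assumed U-shaped 0–12 distribution, change score against adjusted was 53% against 65% at latent rho 0.7 and 68% against 77% at 0.8, so the cut-offs are not general. The plan's fallback to transformation or nonparametric methods was not evaluated. With dropout, the compound-symmetry mixed model and the change-score ANOVA reach the same decision in 92–99% of trials when there is an effect, so they are close but not identical. Type I error of up to 5.5% for the planned model in B and for the regression in A is slightly more than simulation error would explain, but trivial. None of this favours leaving baseline out.

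**Conclusion.** The point holds as a nearly free improvement, not as an error. Conditioning on baseline-session drinks gains about 9–16 points of power at rho 0.3–0.5, 3–5 points at 0.6–0.7 and 1 point at 0.8. These figures assume equal session SDs, a 0.8-SD effect, 52 completers and roughly bell-shaped drinks. With a post-treatment SD of 3.9 against 3 at baseline, the gain falls to 9 points at rho 0.3 and none at 0.8. It barely depends on which stratification or completer count is used.

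Confidence is medium, because rho and the SDs are unknown. That uncertainty favours pre-specifying adjustment: it gains when rho is low, and in the scenarios run it lost no more than simulation error when rho was high.

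**What to change.** Make the primary Aim 2 analysis a regression of second-session drinks on treatment, continuous baseline-session drinks and gender. Keep the change-score ANOVA as a sensitivity analysis only. This also settles which analysis decides the aim.

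If a mixed model is preferred, constrain the baseline means to be equal across arms, cross gender with session, and fix an unstructured 2×2 covariance in advance. In scenario A this has power of 79, 83, 86, 91, 95 and 99% across rho 0.3–0.8, with type I error of 5.1–5.5%. Exempt this model from the information-criterion choice of covariance. With a post-treatment SD of 3.9, its type I error is 6.5–7.5% under compound symmetry and 5.5–6.4% under AIC choice, against 5.1–5.5% unstructured.

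Separately, reconcile the stratification variables in Section V.2 and Section V.11. Also reconcile the completer count, which is 52 in Section V.11 and 50 in Sections V.2, V.4 ("we anticipate a final completer sample of 50 heavy drinkers") and VII.1. The recommendation depends on neither.

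The cost is SAP wording and about 2 degrees of freedom (critical t 2.009 at 50 df, 2.011 at 48 df). Both covariates are already recorded.
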